The absolute change from extension study baseline in UAS7 score at Week 12 will be summarized descriptively, it will be provided together with 95% confidence interval. The change from extension study in UAS7 components (ISS7 and HSS7) will also be provided in descriptive manner at Week 12.

Similar missing data imputation rules as the primary endpoint analysis based on change from baseline in UAS7 score at week 12 will be used for this secondary endpoint analyses. The imputations for ISS7 and HSS7 will follow the same missing data imputation rules.

- Percentage of subjects achieving DLQI = 0-1 (no impact on subjects QoL) at Week 12 after retreatment of ligelizumab for subjects receiving the same dose regimen as in the core studies.

An overall score will be calculated according to the scoring manual. The proportion of subjects with overall DLQI scores ≤ 1 at Week 12 will be summarized in a descriptive manner, it will be provided together with a 95% Clopper-Pearson exact confidence interval. Similar missing data imputation rules as the primary endpoint analysis will be applied in this secondary efficacy endpoint analysis. The missing data imputation will be based on the proportion of subject with UAS7 = 0 at week 12.

- Cumulative number of weeks that subjects achieve AAS7 = 0 between extension study baseline and Week 12

The cumulative number of weeks achieving AAS7 = 0 response between baseline and Week 12 will be derived based on the AAS eDiary. A weekly AAS7 score will be derived by adding up the daily scores of the 7 days preceding the visit, and ranges from 0 to 105. For a weekly AAS7 score, if one or more of the daily scores are missing, the same principles as handling the weekly score from UPDD will be applied to handle the missing data. If the AAS7 score is missing, similar missing imputation rules as the primary analysis will be applied on AAS7 = 0 proportion over the first 12 weeks. The imputed AAS7 = 0 will be used for the cumulative number of weeks that subjects achieve AAS7 = 0 response calculation. The cumulative frequency plot will be provided together with the summary statistics.

- Percentage of subjects achieving UAS7 ≤ 6 (well-controlled urticaria) at 12 weeks after starting self-administration in the first half of the treatment period.

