2.6.3 Handling of missing values/censoring/discontinuations

Missing data handling for HSS7, ISS7, and UAS7 score

Refer to Section 2.5.3.

Missing data handling for AAS7 score

The weekly score AAS7 will be derived by adding up the daily scores of the 7 days preceding the visit. The weekly score will then range from 0 to 105.

For each weekly score from AAS, if one or more of the daily scores are missing, then the following principles will be applied to handle the missing data:

- If a patient has at least 4 non-missing daily scores within the 7 days prior to the study visit, then the weekly score will be calculated as the sum of the available eDiary scores of that week, divided by the number of non-missing days multiplied by 7.
- If there are less than 4 non-missing daily scores within the prior 7 days, then the weekly score will be missing for that week.

Missing data handling for DLQI score

There was a very high success rate of accurate completion of the DLQI. However, if responses were incomplete, the following rules were applied:

1. If one question was left unanswered, then the missing value was imputed to a 0 score and the overall DLQI/CDLQI score was summed up in the usual way out of 30.
2. If two or more questions were left unanswered, then the questionnaire was not scored (left to missing).
3. If question no. 7 was answered 'yes', then it was scored to a value of '3'. If question no. 7 was answered 'not relevant' then the score was 0. If question was answered 'no' (not being preventing to work or study) but the skin was a problem for working or studying, then the scores per possible response were either 'a lot' (2) or 'a little' (1) or not at all (0).

Missing data imputation for UAS7=0, UAS7≤ 6, DLQI=0-1, and AAS7=0 response

In analyses of above mentioned secondary efficacy endpoints, missing values with respect to response variables based on UAS7 score, DLQI/CDLQI score will be imputed as described in Section 2.6.1.

Multiple imputation methods refer to Section 2.5.3.

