5.5.2.2 Secondary analysis for binary endpoints

For binary endpoints of UAS7=0/DLQI 0-1 at Week 12, the secondary analysis will be performed based on the data after the missing data imputation for the intercurrent events has been performed.

The SAS procedure `proc mi` will be used for multiple imputation with the following sample code:

```
proc mi data=... out=... nimpute=... seed=123;  
by group;cuin  
class ige cuind group week12;  
fcs logistic (week12 = ige cuind group baseline / details);  
var ige cuind group baseline week12;  
run;  
where group = treatment group  
    ige = baseline IgE
```

cuind = baseline CU index
baseline = baseline UAS7 score
week12 = binary response of UAS7=0/DLQI 0-1 at Week 12 in TRT1.

If the imputation model does not converge, remove the covariates as needed until it converges.

The SAS procedure `proc freq`, and `proc mianalyze` will be used for the analysis. Sample code refer to Section 5.5.1. Wilson score method is not necessary for 95% confidence limits calculation in secondary analysis. Other methods could be performed as needed.

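### SAP 2.6.1 names the wrong endpoint, UAS7 = 0, as the basis for imputing missing DLQI 0-1 responses and so conflicts with SAP 5.5.2.2

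*SAP*

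**What the plan says.** SAP Section 2.6.1 introduces the endpoint with "The proportion of subjects with overall DLQI scores ≤ 1 at Week 12 will be summarized in a descriptive" manner. It then says that rules similar to those for the primary endpoint apply, and adds: "The missing data imputation will be based on the proportion of subject with UAS7 = 0 at week 12". The UAS7 = 0 paragraph of the same section closes with the identical sentence.

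Section 2.6.3 has a block on imputing the binary responses. It gives no rule of its own for a missing DLQI response: "missing values with respect to response variables based on UAS7 score, DLQI/CDLQI score will be imputed as described in Section 2.6.1".

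Section 5.5.2.2 gives sample code for the binary secondary endpoints. The imputed variable is defined as "week12 = binary response of UAS7=0/DLQI 0-1 at Week 12 in TRT1", and the model line is "fcs logistic (week12 = ige cuind group baseline / details". In that model "baseline = baseline UAS7 score".

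The primary-endpoint rules in Section 2.5.3 divide missing data in two. Intermittent missing values, and those caused by early termination of the study, are multiply imputed within treatment arm under missing at random. Everything else counts as non-response.

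**The concern.** DLQI 0-1 and UAS7 = 0 are different events. DLQI is a ten-item quality-of-life questionnaire with a seven-day recall, given to adults only; UAS7 is a weekly score built from twice-daily itch and hives entries. Nothing in the documents says that the two response rates are equal or that one can stand in for the other.

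The rule will be used. The study was stopped early, and SAP Amendment 2 added multiple imputation for the resulting missing data to some key secondary endpoints. A programmer working from the body of the SAP reaches one basis for imputing DLQI, and a programmer working from the appendix reaches another. What is at stake is that a pre-specified key secondary endpoint should have a single imputation rule, fixed before results are seen. If the body text were applied literally, the reported DLQI proportion could also shift.

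**Working it through.** **Comparison of the texts.** The plan states no figure that depends on this rule, so there is nothing to reproduce. The endpoints in Section 2.6.1 compare as follows.

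| Endpoint | Basis of imputation in SAP 2.6.1 | Own variable? |
|---|---|---|
| UAS7 = 0 at Week 12 | UAS7 = 0 proportion | yes |
| Change in UAS7 (ISS7, HSS7 by the same rules) | change from baseline in UAS7 | yes |
| AAS7 = 0, cumulative weeks | similar rules "applied on AAS7 = 0 proportion over the first 12 weeks" | yes |
| UAS7 ≤ 6 after self-administration | non-responder | not applicable |
| DLQI 0-1 at Week 12 | UAS7 = 0 proportion | **no** |

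DLQI is the only endpoint tied to another endpoint's response. No reason is given, and the sentence matches the UAS7 = 0 paragraph word for word. That points to a copied sentence.

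**Does another section settle it?**
- Section 2.6.3 refers back to 2.6.1, and Section 2.14.8 applies 2.5.3 and 2.6.3 to the final analysis. The chain in the body text therefore ends at the faulty sentence.
- Section 5.5.2.2 imputes "binary response of UAS7=0/DLQI 0-1 at Week 12 in TRT1". The slash is naturally read as one run per endpoint. The predictors are IgE, CU index, treatment group and baseline UAS7. Week 12 UAS7 = 0 is not among them, so a missing DLQI response is drawn from a model fitted to observed DLQI 0-1 responses.
- Protocol Section 12.5.1 treats a missing DLQI response as non-response, and SAP Section 4 records no change from the protocol. Neither shows which basis was meant for the multiply imputed part.

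**Size under a literal reading.** Let f be the share of subjects whose DLQI response is multiply imputed, pU the UAS7 = 0 rate and pD the DLQI 0-1 rate. Filling the share f at rate pU instead of pD changes the reported proportion by

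shift = f × (pU − pD).

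The share f covers only data that are multiply imputed. Subjects set to non-response are unaffected by the sentence.

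Inputs:
- pU: 44.0%, borrowed for illustration from the Phase IIb 72 mg arm after the third dose (Protocol Section 4.1.1).
- pD: no value in the documents; 40% to 65% assumed.
- f: no value in the documents; 5% to 20% assumed. The 10% drop-out planned at Week 12 (15% for the responder subgroup; Protocol 12.8.1, SAP 3.1) predates termination and does not separate the two kinds of missing data.

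| f | pD = 40% | pD = 65% |
|---|---|---|
| 5% | 0.05 × (44 − 40) = +0.2 points | 0.05 × (44 − 65) = −1.05 points |
| 20% | 0.20 × (44 − 40) = +0.8 points | 0.20 × (44 − 65) = −4.2 points |

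The shift is zero if nothing is multiply imputed or if the two rates are equal. Its direction depends on which rate is higher, which the documents do not say.

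**The case against.** The strongest reply is that this is a wording slip and that the correct specification is already in the SAP. According to the change logs, the sample code came with Amendment 3, after Amendment 2 had added multiple imputation to Section 2.6. The later and more detailed text imputes the right variable, and a programmer who follows it gets a sensible result. The disputed sentence also gives no procedure for filling a DLQI response from a UAS7 = 0 proportion. It may only have been meant to set the scale of imputation: the primary endpoint imputes a continuous change and then dichotomises, whereas these endpoints are imputed directly as binary responses. On that reading only the endpoint label is wrong.

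Most of this stands as an account of how the sentence arose and why the practical risk is low. It does not remove the conflict. The text never says that the sentence is about scale, the code is offered as a sample, and the body of the SAP leads back to the wrong label.

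A reader might infer more: that the sponsor chose to impute quality of life from symptom control, or that the DLQI result will be biased by, say, 1 to 3 points (a 10 to 15 point gap in rates times 10 to 20% imputed). The documents support neither. No passage argues for such a choice, and the appendix does the opposite. The gap and the share are both assumed, and non-responder data lie outside the calculation.

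**Conclusion.** The point holds as an internal inconsistency. The DLQI paragraph of Section 2.6.1 names the wrong endpoint as its basis of imputation, Section 2.6.3 leads back to it, and Section 5.5.2.2 contradicts it. It should be corrected because the rule applies in the final analysis of a key secondary endpoint.

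The size of any effect is unknown and may be near zero. It arises only if the sentence is programmed literally against the SAP's own code, only for the multiply imputed share, and only to the extent that the two rates differ. The shifts shown above rest on a borrowed UAS7 = 0 rate, an assumed DLQI rate and an assumed share, and should not be read as estimates. Section 2.6.2 plans no inferential methods, so no test or decision depends on the result.

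The appendix model adjusts DLQI for baseline UAS7 and not baseline DLQI. That is a separate modelling choice to confirm and has no bearing on this conclusion.

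**What to change.** In the DLQI paragraph of SAP Section 2.6.1, change UAS7 = 0 to DLQI = 0-1 in the imputation sentence and add a reference to Section 5.5.2.2. Leave the preceding sentence on primary-endpoint rules in place, so that:

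- intermittent and early-termination missingness is multiply imputed on the DLQI 0-1 response within treatment arm;
- all other missing data remain non-responder, as in Section 2.5.3.

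The limit matters. A general statement that every missing DLQI response is imputed from observed responses in the same arm would override non-responder imputation for subjects who stopped for adverse events or lack of efficacy and have no retrieved data. Nothing needs adding on age groups, because Section 5.1.2 already analyses DLQI in adults and CDLQI in adolescents separately. Section 2.6.3 needs no edit once 2.6.1 is right.

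The cost is one sentence, with no change to data collection, sample size or the sample code.

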Section 2.3	
Text updated: “Information on screen-failed subjects will not be included in the summaries of demographics, disease characteristics at baseline, and medical history.”
 
“Baseline proportion of AAS7 = 0” was added to the baseline disease characteristics.
 
“Duration of a typical angioedema episode – collected at Visit 201”, “Experienced angioedema within the past 4 weeks – collected at Visit 201”, and “Duration of the last episode of angioedema – collected at Visit 201” were removed, because those information are not collected as per protocol.
 
Text updated: “In addition, duration of study periods TRT1, OBS2, TRT2, FU12 and FU52 will be summarized by treatment group for FAS; duration of study period OBS1 will be summarized for ENR.”

Section 2.4	
Text updated: “Concomitant medications are defined as any medication given at least once between the first dose of the

	study treatment and the date of the last study visit in the extension study.”
Section 2.5	
For subjects rolling over from study CQGE031C2302 and CQGE031C2303, who received different treatment or different ligelizumab dose regimen, removed text: “The efficacy data for these subjects will be analyzed separately.”
 
For subjects rolling over from study CQGE031C1301, who received ligelizumab 120 mg, removed text: “The efficacy data for these subjects will be analyzed separately.”
 
For subjects rolling over from the adolescent PK/PD study CQGE031C2202, removed text: “The efficacy data for these subjects will be analyzed separately.”
 
Removed Section 2.5.4, the supportive analyses of adolescent subjects versus adult subjects.
 
Added primary estimand, and added multiple imputation for missing data due to study early termination.

Section 2.6	Added multiple imputation for missing data due to study early termination for some key secondary endpoints.
Section 2.8	The analysis scope of AEs, AESIs, lab, ECG and vital signs was updated according to the final analysis.
	
	
Section 2.11	
Removed text: “Number and proportion of subjects with values outside of the limits of quantification will be presented.”
 
Added text: “The unscheduled visit information will not be included in the summary table.”
 
Text updated: “A summary table will be provided for baseline values by treatment group. The unscheduled visit information will not be included in the summary table.”

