
To describe the efficacy of ligelizumab in the treatment of CSU, 12 weeks after starting self-administration	
The proportion of subjects with well-controlled disease ($UAS7 \leq 6$), 12 weeks after starting self-administration
For safety & tolerability evaluation:	

To assess the safety and tolerability of ligelizumab in all subjects	
In each dose group, and for each duration of treatment:
 
Occurrence of treatment emergent adverse events during the studyOccurrence of treatment emergent serious adverse events during the studyVital signsLab assessments

To assess the safety and tolerability of ligelizumab 120 mg q4w 1mL pre-filled syringe (PFS)	
For the duration of treatment:
 
Occurrence of treatment emergent serious adverse events during study Week 12 onwardsVital signs Week 12 onwardsLab assessments Week 12 onwards

To assess the safety and tolerability of ligelizumab 120 mg q4w in all subjects who self-administer	
Occurrence of treatment emergent adverse eventsOccurrence of treatment emergent serious adverse eventsVital signsLab assessments

Objective(s)

Endpoint(s)

On 06 April 2022, following extensive assessment of data from the Phase III studies (CQGE031C2302, CQGE031C2303) of ligelizumab in CSU, Novartis communicated a strategic decision to discontinue further clinical development of ligelizumab in chronic urticaria (CSU and chronic inducible urticaria (CINDU)). The decision to not proceed was not based on

any safety concerns with ligelizumab. As a result of this decision, this study CQGE031C2302E1 was terminated.

2 Statistical methods

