2.5.3 Handling of missing values/censoring/discontinuations

The UAS7 score is derived from the sum of the HSS7 score and the ISS7 score, as noted above. The HSS7 and ISS7 score will be derived by adding up the daily HSS and ISS scores of the 7 days preceding the visit, respectively. The daily score (HSS and ISS) will be calculated by averaging the morning and evening HSS and ISS score, respectively. If one of the morning or evening scores is missing, the non-missing score for that day (morning or evening) will then be used as the daily score.

A minimum of 4 out of 7 daily scores are needed to reliably calculate a weekly HSS7, ISS7 or UAS7 score. For each weekly score from UPDD (i.e. HSS7, ISS7 and UAS7 score), if one or more of the daily scores are missing, the following principles will be applied to handle the missing data:

- If a subject has at least 4 “non-missing” daily scores within the 7 days prior to the study visit, the weekly score will be calculated as the sum of the available eDiary scores of that week, divided by the number of non-missing days, multiplied by 7.
- If there are less than 4 “non-missing” daily scores within the prior 7 days, then the weekly score will be considered as missing for that week.

Subjects who discontinue from study treatment early will be encouraged to stay in the study following the procedures described in the study protocol Section 9.1.1. These are considered as retrieved dropout (RDO) subjects.

The primary analysis will account for different post-dosing events for missing data handling as follows:

- Discontinuation of initially assigned study treatment prior to Week 12 (Visit 204) due to AEs or lack of efficacy or any other reasons, except for the reason of study early termination: Retrieved dropout (RDO) data collected after study treatment discontinuation will be used for analysis. If no RDO data was collected after study treatment permanent discontinuation, non-responder imputation will be applied for missing data imputation.
- Discontinuation of initially assigned study treatment prior to Week 12 (Visit 204) due to study early termination: the efficacy data collected after the discontinued treatment will be censored. The missing data caused by this intercurrent event occurrence will be imputed based on the treatment arm (ligelizumab 72 mg or 120 mg q4w) data under the missing at random (MAR) assumption using multiple imputation separately.

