The proportion of subjects with UAS7 ≤ 6 , 12 weeks after starting self-administration will be summarized in a descriptive manner, and it will be provided together with 95% Clopper-Pearson exact confidence interval. Missing data will be considered as non-responder in the analysis.

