2.14.8 Handling of missing values/censoring/discontinuations

The missing data handling and imputation rules as described in Section 2.5.3 and Section 2.6.3 will be applied on the primary and some key secondary endpoints, respectively. All the other analyses in the final analysis will be based on the observed data.

Table 2-16 Overview of final analysis

Population/ Analysis /Study Period	Endpoints
First treatment period (TRT1)	
Analysis: Efficacy Populations: 1) FAS 2) Ligelizumab retreatment subpopulation 3) Ligelizumab responder retreatment subpopulation Period/time point: TRT1/up to week 52	
• Proportion of subjects with well-controlled urticaria ($UAS7 \leq 6$) at Week 12

Analysis: Efficacy
 
Populations:
 
 1) FAS 2) Ligelizumab retreatment subpopulation 
Period/time point: TRT1/up to week 52
	
 • Proportion of subjects with completely controlled disease (UAS7 = 0) at Week 12

Analysis: Efficacy
 
Populations:
 
 1) FAS 2) Ligelizumab retreatment subpopulation 
Period/time point: TRT1/up to week 52
	
 • Absolute and percent change from extension study baseline in the UAS7 and its components (ISS7 and HSS7) at Week 12 • Percentage of subjects achieving DLQI = 0-1 at Week 12

Analysis: Efficacy
 
Populations:
 
 1) FAS 2) Ligelizumab retreatment subpopulation 
Period/time point: TRT1A/up to week 12
	
 • Cumulative number of weeks that subjects achieve weekly angioedema activity score (AAS7) = 0 between extension study baseline and Week 12

Analysis: Efficacy
 
Population: Self-administration subpopulation
 
Period/time point: 12 weeks after starting self-administration in TRT1
	
 • The proportion of subjects with well-controlled disease (UAS7 ≤ 6), 12 weeks after starting self-administration

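### The self-administration endpoint counts a 12-week UAS7 that is missing because of the sponsor's termination as non-response, unlike every other Week 12 efficacy endpoint, and SAP 2.6.1 and 2.14.8 can be read as different rules for it

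*SAP*

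**What the plan says.** - **Rule for this endpoint.** The last item of SAP 2.6.1 covers the proportion with UAS7 ≤ 6 at 12 weeks after starting self-administration, with a Clopper-Pearson interval. It states: "Missing data will be considered as non-responder in the analysis". Protocol 12.5.1, written before the termination, has the same rule.
- **Termination.** SAP 1.2 records the sponsor's strategic decision, which was not based on safety: "As a result of this decision, this study CQGE031C2302E1 was terminated".
- **Rule for the primary endpoint.** SAP 2.5.1.1 assigns termination a hypothetical strategy. SAP 2.5.3 censors efficacy data after the stop and adds "The missing data caused by this intercurrent event occurrence will be imputed based on the treatment arm", under missing at random. That bullet is limited to discontinuation before Week 12 (Visit 204). Scores missing for all other reasons are non-response.
- **Rule for the other secondary endpoints.** For UAS7 = 0 and for DLQI 0-1, SAP 2.6.1 says "Similar missing data imputation rules as the primary endpoint analysis will be applied in this secondary efficacy endpoint analysis". Similar wording covers change in UAS7, ISS7 and HSS7, and AAS7 = 0.
- **Scope of the change.** The Amendment 2 log entry for Section 2.6 reads "Added multiple imputation for missing data due to study early termination for some key secondary endpoints".
- **Final analysis.** Table 2-16 keeps the endpoint, timed "12 weeks after starting self-administration in TRT1". The text of 2.14.8 above that table applies the imputation rules to the primary and some unnamed key secondary endpoints, and puts all other analyses on observed data.

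**The concern.** Under Amendment 2, a stop caused by the sponsor's decision is treated as uninformative about response, and the primary endpoint and the other Table 2-9 endpoints are imputed accordingly. The self-administration endpoint reads out later, so a subject who had passed Week 12 safely could still be cut off before it. The plan scores such a subject as a failure if no UAS7 can be calculated. Nothing is tested (SAP 2.6.2), so the rule is not conservative in any useful sense: it only lowers a descriptive rate for an administrative cause. This is also the only efficacy endpoint listed for the self-administration objective.

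**Working it through.** **1. Which rule applies.** The sections were traced in turn.

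| Place in SAP | What it does for self-administration |
|---|---|
| 2.6.1 | Non-response for all missing data |
| 2.6.3 | Sends UAS7-based responses back: "missing values with respect to response variables based on UAS7 score, DLQI/CDLQI score will be imputed as described in Section 2.6.1" |
| 2.5.3, termination bullet | Does not reach it: limited to stops before Visit 204, and self-administration starts at Visit 204 or later (protocol 6.7.2) |
| 2.5.3, all other reasons | Non-response |
| 5.5.2.2, imputation code | Introduced by "For binary endpoints of UAS7=0/DLQI 0-1 at Week 12"; no code for this endpoint |
| 2.14.8 | Observed data, if this endpoint is not among the unnamed ones |

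The endpoint-specific text points to non-response. The general sentence in 2.14.8 is weaker, but it is not reconciled with 2.6.1.

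**2. Who can be affected.** These are subjects who had started self-administration but were less than 12 weeks past the start when treatment stopped. The start is defined in two ways. SAP 2.6 and Table 2-9 count from the outside-clinic start (Week 24, read-out about Week 36). SAP 2.14.1 and Table 2-16 use a population that self-administers in clinic or outside (start possible at Week 12, read-out about Week 24).

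**3. Whether their score is missing.**
- Protocol 9.1.5 handles terminated subjects as treatment discontinuers.
- Protocol 9.1.1 plans EOT 4 weeks after the last dose and Visit 9999 a further 12 weeks later: 4 + 12 = 16 weeks.
- Protocol 3.6 keeps the eDiary going in follow-up.
- The last dose cannot precede the first self-administered dose, so the 12-week point falls at most 12 weeks after the last dose, inside the planned 16.

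A score is therefore missing only if fewer than 4 daily scores exist in that week (2.5.3). Where a score exists, it comes from after treatment stopped, and no rule censors it for this endpoint.

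**4. Size of the non-response effect.** The plan states no figure for this endpoint. The nearest is SAP Table 3-1, at 55% with 10% drop-out. It reproduces as plain Wald intervals on 124/225, 223/405 and 297/540: 48.6–61.6%, 50.2–59.9% and 50.8–59.2%. It serves here only as the source of 55%, which is a Week 12 planning rate.

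Let m be the share of the analysis population with no calculable 12-week UAS7 because of termination. If these subjects would have responded like the rest:

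expected reported rate = p × (1 − m), so bias = −p × m.

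| m (assumed) | Expected rate at p = 55% | Bias at 55% | Bias at p = 70% (assumed) |
|---|---|---|---|
| 5% | 52.25% | −2.75 points | −3.5 points |
| 10% | 49.5% | −5.5 points | −7 points |
| 20% | 44.0% | −11 points | −14 points |

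Example with an assumed N = 200, p = 55% and m = 20%: 160 subjects are observed and 88 respond. Non-responder scoring gives 88/200 = 44.0% (Clopper-Pearson 37.0–51.2%), an interval that excludes 55%. Among those observed, 88/160 = 55.0% (46.9–62.9%). The latter is the missing-at-random point estimate; an imputation interval would differ somewhat.

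**The case against.** The strongest reply is that the missing scores may hardly exist. A reader might infer that every subject whose 12-week point fell after the stop is scored as a failure. The documents do not support that, because follow-up visits and diary entries are planned past the 12-week point, SAP Table 2-1 assigns study weeks to that follow-up, and SAP 2.14 runs the final analysis after all last visits. This stands, and it is why m is defined by calculable scores. It does not settle the matter. The documents do not say whether sites kept the schedule, and protocol 9.2 dates study completion to the decision itself in the event of early termination. If the diaries were kept, the problem changes form: off-treatment scores enter a rate meant to describe self-administered treatment, whereas 2.5.3 censors such data for the primary endpoint.

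A second reply is that 2.14.8 may put the endpoint on observed data, so nobody is scored as a failure. The text of 2.6.1 makes this the weaker reading, but it is a possible one, and the conflict is itself part of the point.

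Third, the log entry limits imputation to some endpoints, so the omission may be deliberate. That may be so, but no reason is given for treating one cause of missingness in two ways.

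Fourth, lack of comparability with the Week 12 rate is a weak complaint. The populations and time points already differ and no comparison is planned. Observed-data UAS7 ≤ 6 rates by visit are also specified for the self-administration subpopulations in the unplanned interim analysis (SAP 2.13.2.4). Both points stand and lower the severity.

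**Conclusion.** The concern holds with limits. As written, SAP 2.6.1 counts a termination-caused missing 12-week UAS7 as failure, and no endpoint-specific text elsewhere overrides it. The expected loss is p × m: 2.75 to 11 points at 55% for m of 5% to 20%, and near zero if follow-up diaries give calculable scores. This rests on three assumptions: affected subjects would have responded like the others, 55% carries over from Week 12, and the values of m are illustrative because the documents give none. Subjects with a follow-up score are instead counted on off-treatment data; the documents do not allow that effect to be sized.

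A reader might infer a demonstrated large bias in the reported rate, or a defect that must be cured before any analysis. Neither is supported: m is unknown, and the endpoint is secondary and descriptive with no test. Severity is moderate.

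**What to change.** In SAP 2.6.1, state for this endpoint:

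1. **One start of self-administration**, reconciling the outside-clinic definition (2.6, Table 2-9) with the in-clinic-or-outside one (2.14.1, Table 2-16).
2. **A termination rule anchored to 12 weeks after that start**: censor efficacy data collected after a treatment stop caused by study termination, and impute the 12-week value by multiple imputation under missing at random.
3. **Other reasons for discontinuation**: use retrieved drop-out data where they exist, and non-response otherwise.
4. **An interval that suits imputed data**, combined across imputations as in 5.5.2.2.

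Then name in 2.14.8 the key secondary endpoints to which imputation applies, so that this one is not left on observed data by default. Report how many subjects had their 12-week assessment affected by termination, split into no calculable score and off-treatment score only.

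Pointing to 2.5.3 as it stands would not work, because its termination bullet ends at Visit 204 and its fallback is non-response. The cost is a short SAP paragraph and a small adaptation of the imputation program in 5.5.1, which now imputes the Week 12 change and would need the new time point and population. No new data are needed.
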